9.2 Administrative and Regulatory Considerations

9.2.1 Good Clinical Practice

The study will be conducted in accordance with good clinical practice (ICH GCP) and all applicable regulations including the ethical principles of the Declaration of Helsinki (Edinburgh 2000, with Note of Clarification, Tokyo 2004).

9.2.2 Informed Consent

The Sponsor or designee will provide the Investigator with a template ICF for the study, which may be modified for local use. A study team member authorized to obtain consent will obtain a written ICF from each study subject prior to the performance of any study-related procedures.

Consent will be obtained only after full disclosure of the nature of the study, its risks and benefits, in accordance with local and federal regulations and guidelines. The fact that informed consent was obtained, and the date upon which it was obtained, will be documented in each subject's study records.

If the ICF is amended at any time during the study, the Investigator must follow all applicable regulatory requirements to ensure review and approval of the amended consent form by the IRB/IEC. Subjects must sign the most current IRB/IEC-approved version of the ICF at the time of their participation in the study.

9.2.3 Ethical Review

The Investigator or designee will prepare and submit all required documentation and obtain local IRB/IEC approval to implement the study prior to the conduct of any study procedures. At a minimum, the study protocol, ICF, Investigator's Brochure, and study-related advertisements and promotional materials will be submitted.

If it is necessary to amend the protocol and/or ICF during the course of the study, the Investigator must ensure that the IRB/IEC reviews and approves these amended documents. No amendments to the study protocol should be made without the agreement of the Investigator and Sponsor as well as the IRB/IEC, where applicable.

The Investigator will maintain documentation of the composition of the IRB/IEC as well as all correspondence with the IRB/IEC. The Investigator will comply with local requirements for routine reporting to the IRB/IEC, as well as local and government requirements for notifying the IRB/IEC of SAEs. The Investigator will prepare a final study report and submit it to the IRB/IEC within 3 months of study completion. The Investigator or designee will provide Sponsor or designee with copies of IRB/IEC approval notices, correspondence, annual reports, and final study reports.

9.2.4 Protocol Compliance

The study will be conducted in compliance with the protocol. The Investigator is responsible for ensuring compliance by all study staff members. Deviations from protocol-specified procedures will be documented in subjects' study records.

10 DATA COLLECTION, SITE MONITORING, AND ADVERSE EXPERIENCE REPORTING

10.1 Data Management

Site personnel will collect, transcribe, correct, and transmit the data onto source documents, CRFs, and other forms used to report, track and record clinical research data. The clinical site will be monitored to ensure compliance with data management requirements and Good Clinical Practices. All study data will be collected via systems that comply with all applicable guidelines regarding patient confidentiality and data integrity.

10.1.1 Registration

Registration of participants on this protocol will employ an interactive data system in which the clinical study site will attest to the participant's eligibility as per protocol criteria and obtain appropriate informed consent. IRB approval for the protocol must be on file at the institution before accrual can occur from the clinical study site.

A system of coded identifiers will be used to protect participant confidentiality. When the participant is registered to participate in the study, the system will assign a participant ID number. To confirm the correct participant ID, the data entry system will require a second entry of the unique participant ID and compare for consistency. In this fashion, no personal identifiers would be accessible and the data will be collected on the correctly identified subject.

10.1.2 Documentation of Data

As part of the responsibilities assumed by participating in the study, the Investigator agrees to maintain timely case histories for the subjects treated as part of the research under this protocol, including accurate source documentation. A CFR21, part 11 compliant electronic data capture system for source data will be developed and provided for use in the clinical study. The majority of source data will be recorded directly into data capture system; however some source data, including, but not limited to, AEs, concomitant medications and protocol deviations will be recorded on paper-based source documents. Paper-based data will be entered into a separate clinical database, and will be merged with the electronic data capture system during processing and analysis. ECG readings are printed with a machine interpretation on the ECG. This is then reviewed by the study investigator. If there is a question with the interpretation, the investigator can ask a cardiologist for another read.

ECG data will be forwarded electronically for inclusion in data reporting and analyses. The Investigator will be responsible for ensuring that adequate checks are carried out on all study data.

At the completion of the study, the Sponsor will receive a complete set of data for all subjects.

10.1.3 Source Document Verification

All (100%) subject data (electronic and paper-based source) will be reviewed by the monitors for accuracy and consistency. This will be conducted with due regard to subject confidentiality.

10.2 Data Management

Data collection processes and procedures will be reviewed and validated to ensure completeness, accuracy, reliability, and consistency. A complete audit trail will be maintained of all data changes. Electronic consistency checks and manual review will be used to identify errors or inconsistencies. This information will be provided to the study site by means of electronic or manual queries.

10.2.1 Monitoring the Study Data

The conduct of the study will be monitored by the Sponsor, or designee, to ensure compliance with applicable regulatory requirements and GCP. The study monitor will maintain necessary telephone and letter contact with the Investigative site. The study monitor will verify that the study is conducted in accordance with the currently approved protocol and any amendments and will monitor subject enrolment, completeness and accuracy of subject data and reporting and recording of AEs.

The monitor will maintain current knowledge of the study through observation, review of study records and discussion of the conduct of the study with the Investigator and staff. Monitoring will be conducted according to Good Clinical Practice and applicable government regulations. The investigator agrees to allow monitors access to the clinical supplies, dispensing and storage areas, and to the clinical files of the study subjects, and, if requested, agrees to assist the monitors.

Safety monitoring will include careful assessment and appropriate reporting of adverse events. Medical monitoring will include contemporaneous assessment of serious adverse events.

The DSMB will meet after each cohort is completed or as needed, and will review subject recruitment, AE's, side effects, withdrawals, protocol violations, and inclusion/exclusion criteria. More frequent meetings will take place if necessary. Roles and responsibilities for the DSMB will be outlined in a separate DSMB charter document.

The Safety Monitor will review all adverse events, in a blinded fashion, on a periodic basis. In addition, the monitor will review all events that meet the regulatory definition of a Serious Adverse Event, upon receipt of notification via the Electronic Data Capture (EDC) system.

An adverse event (AE) is any unfavorable and unintended sign (including a clinically significant abnormal laboratory finding, for example), symptom, or disease temporally associated with a study, use of a drug product or device whether or not considered related to the drug product or device. FDA, Office of Human Research Protection (OHRP), and IRB requirements for reporting AEs will be followed. Subjects will be monitored for AEs from the time they sign consent until 30 days following permanent discontinuation of study drug. At that point, all ongoing AEs will be followed to resolution, but no new AEs will be recorded. The monitor/DSMB will review cumulative AEs; the frequency of this review will be determined by the monitor/DSMB in conjunction with the Protocol PI.

The Clinical Site Medical Monitor and research team (co-Investigators, research nurse, clinical trial coordinator) are responsible for identifying and reporting AEs and determining the relationship of the event to the study drug/study procedures. Aggregate reports blinded by treatment group, detailed by severity, attribution (expected or unexpected), and relationship to the study drug/study procedures, will be available for review by the monitor. A separate report detailing protocol compliance will also be available monthly for review by the Protocol PI and Safety Monitor, who will provide feedback to the site as needed. The Safety Monitor will advise the Protocol PI as to whether the protocol or informed consent document requires revision based on these reports.

10.3 *Inspection of Records*

The Investigator and institution involved in the study will permit trial-related monitoring, audits, IRB/IEC review, and regulatory inspection(s) by providing direct access to all study records, medical files, and source data to enable verification of the trial data. In the event of an audit, the Investigator agrees to allow the Sponsor, the FDA, or other Regulatory Agency access to all study records.

The Investigator should promptly notify the Sponsor of any audits scheduled by any Regulatory Authority and promptly forward copies of any audit reports received to the Sponsor.

10.3.1 Records Retention

In accordance with all applicable regulatory requirements, the Investigator will maintain a copy of all site records in a safe and secure location on completion of the study. The location of the Investigator file archive will be made known to the Sponsor at study conclusion and if the archive location changes, the Investigator will notify the Sponsor. Sponsor will archive study data according to their normal practice.

10.3.2 Quality Assurance

The Investigator site, facilities and all data and documentation may be audited by an independent auditor. The Investigator must allow the auditor access to all relevant documents and be available to discuss any findings/issues.

11 HUMAN SUBJECTS

Documented approval from the IRB will be obtained prior to clinical trial start, according to ICH GCP, local laws, regulations and organization. When necessary, an extension, amendment or renewal of the IRB approval must be obtained.

Evidence of training in responsible conduct of research shall be on file for each site PI and co-investigators.

11.1 Institutional Review Board (IRB) Review and Informed Consent

This protocol and the informed consent document and any subsequent modifications will be reviewed and approved by the IRB responsible for oversight of the study. A signed consent form, approved by the IRB, will be obtained from the subject. The consent form will describe the purpose of the study, the procedures to be followed, and the risks and benefits of participation. A copy of the consent form will be given to the subject, parent, or legal guardian, and this fact will be documented in the subject's record.

11.2 Subject Confidentiality

All laboratory specimens, evaluation forms, reports, video recordings, and other records that leave the clinical study site will be identified only by the study specific Subject Identification Number (SID) to maintain subject confidentiality. All records will be kept in a locked file cabinet. All computer entry and networking programs will be done using study specific SIDs only.

Clinical information will not be released without written permission of the subject, except as necessary for monitoring by IRB, the FDA, the OHRP, the sponsor, or the sponsor's designee.

11.3 Study Modification/Discontinuation

The study may be modified or discontinued at any time by the IRB, the sponsor, the OHRP, the FDA, or other government agencies as part of their duties to ensure that research subjects are protected.

The present first-in-human study will provide safety and pharmacokinetic (PK) information on single ascending doses (SAD) of MW151 to support decisions for continued clinical development. This study will assess the safety, tolerability, and PK profile of escalating single doses of MW151 in healthy adult participants. The trial design will be a double-blind, placebo-controlled, SAD study of MW151 in healthy volunteers. Five dosing cohorts are initially planned. All subjects and the study personnel responsible for assessing adverse events (AEs) will be blinded. This statistical analysis plan (SAP) provides a more technical and detailed elaboration of the statistical analyses of safety and tolerability data as outlined in the protocol.

In the study design, 40 healthy male and female volunteers, ages 18-50 years, will be dosed in 1 of 5 dosing cohorts of 8 subjects each. Subjects will be admitted to the inpatient clinic on the day prior to dosing (Day -1) and will remain in the unit until discharge on Day 3. A follow-up visit will be done on Day 7.

A single dose of study drug or placebo will be administered as an oral capsule(s) on Day 1. Five different doses of MW151 will be evaluated in 5 sequential cohorts. Dosing will start at the lowest dose, then escalate in the 2nd cohort, then escalate sequentially in the 3rd, 4th, and 5th cohorts.

Cohort 1: Dose1: MW151/101 10 mg (or matched placebo), 1 x 10 mg capsule administered orally.

Cohort 2: Dose2: MW151/101 20 mg (or matched placebo), 1 x 20 mg capsule administered orally.

Cohort 3: Dose3: MW151/101 40 mg (or matched placebo), 2 x 20 mg capsule administered orally.

Cohort 4: Dose4: MW151/101 80 mg (or matched placebo), 1 x 80 mg capsule administered orally.

Cohort 5: Dose5: MW151/101 160 mg (or matched placebo), 2 x 80 mg capsule administered orally.

As a safety consideration, two sentinel subjects in each cohort will be administered MW151 or placebo in a 1:1 ratio. Dosing of the remaining subjects in a cohort may proceed after review of sentinel subject safety and tolerability data collected during the first 24 hours of dosing and

determination that no stopping rules are met. The remaining 6 subjects will be randomized in a 5:1 ratio. The remaining subjects in each cohort will be dosed sequentially, not simultaneously.

After the completion of each cohort (Cohorts 1-5), the Data Safety Monitoring Board (DSMB) will review all available safety data before the dosing of the sentinel subjects of the next cohort.

Data from Cohorts 1-5 will be reviewed in a blinded manner, unless the findings suggest the triggering of a stopping rule, in which case the data for the subjects in question may be unblinded (e.g., if a drug related serious AE [SAE] occurs, identifying whether the subject received MW151 or placebo to determine whether the stopping rule should be triggered). Doses may be varied based on the safety review, but the maximum dose will not exceed 160mg. Should the safety data warrant, dose levels may be reduced or additional cohorts added in order to generate a comprehensive understanding of the clinical dose range. Should additional cohorts be required above the planned 5 cohorts or doses within the planned cohorts changed, a protocol amendment will be submitted to the FDA and the Independent Ethics Committee for approval before implementation.

Screening will be conducted in the 28 days prior to inpatient admission. After giving written informed consent, each subject will undergo a medical screen consisting of the following procedures: demographics; medical history; concomitant medication review; body temperature; 12-lead ECG; vital signs (BP, HR); physical exam; alcohol and drug screen; Hepatitis B, Hepatitis C, HIV, Columbia Suicide Severity Rating Scale and TB screens; and safety laboratory work and pregnancy testing.

One day prior to dosing (Day -1), subjects will be admitted to the Duke Early Phase Research Unit (DEPRU) Phase 1 unit for final qualification assessments. These assessments will include inclusion/exclusion review, medical history, physical exam, infection screen, body temperature, alcohol and drug screen, vital signs, pregnancy test, neurological exam, and safety laboratory tests.

A single dose of study drug or placebo will be administered as an oral capsule(s) on Day 1. During dosing, subjects will be continuously monitored with 12-lead ECG, blood pressure, and heart rate. Plasma samples will be drawn at sequential time points for PK analysis.

Subjects will remain in the clinical research unit until discharge on Day 3. Follow-up will be done through a clinic visit on Day 7. The follow-up visit will consist of safety lab work, body temperature, ECG, vital signs, concomitant medication review, and assessment of adverse events (AEs).

3.0 **OBJECTIVES**

Primary Objective

To assess the safety and tolerability of single ascending doses of MW151 when administered orally to healthy adult volunteers.

The hypothesis is that MW151 will be safe in humans when administered in a SAD paradigm, with no severe or serious adverse events.

Secondary Objective

To assess the PK profile of single ascending doses of MW151 when administered orally to healthy adult volunteers.

4.0 SUBJECT POPULATIONS

Any subject who discontinues the study prior to dose administration for reasons other than AEs may be replaced by a different subject. The replacement subject will receive the same treatment as the original subject.

4.1 RANDOMIZED POPULATION

The Randomized Population will consist of all subjects who sign informed consent and who are randomized to a treatment group in the study.

4.2 SAFETY POPULATION

The Safety Population will consist of all subjects in the Randomized Population who receive any double-blind study medication (MW151 or placebo).

4.3 PK POPULATION

The PK Population and analyses will be defined in the PK Analysis Plan.

5.0**STUDY DISPOSITION**

The number of subjects included in each study population (i.e., Randomized, Safety) will be summarized by cohort and active drug vs. placebo.

The number and percentage of subjects who completed and prematurely discontinued the study will be presented by study drug and overall vs placebo for the Randomized Population. Reasons for premature discontinuation as recorded on the completion page of the CRF will be summarized, as applicable.

6.0**DEMOGRAPHICS AND OTHER BASELINE CHARACTERISTICS**

Demographic parameters (e.g. age, race, sex, weight, height, BMI) and other baseline characteristics, such as medical history, will be summarized by treatment group for the Safety Population. In addition, data listings will be generated.

7.0 STATISTICAL ISSUES

7.1 GENERAL ANALYSIS CONVENTIONS

General statistical approaches are presented below.

All subjects in the Safety Population will be included in the safety analysis grouped by cohort and treatment group. Statistical analysis of safety data will be descriptive.

Baseline is defined as the last assessment prior to dosing of study medication.

For continuous variables, summaries will include sample size, mean, median, standard deviation, minimum, and maximum. For categorical variables, the summaries will include frequencies and corresponding percentages. No inferential hypothesis testing will be performed. Repeat or unscheduled results will not be included in the summaries, but will be listed. Data from placebo subjects will be pooled for final presentations.

Missing data results will not be imputed. Data summaries and analyses (e.g. means) will be calculated using all available data. If the start day for an AE is missing, day of study drug administration will be used and AE will be considered treatment emergent. Neither month nor year will be imputed for AE.

Statistical analyses will be performed in SAS, Version 9.4 or newer.

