Vital Signs (BP, HR, Body Temperature): Summary statistics for BP and HR and change from baseline (predose) summaries will be presented for each treatment group and dose level where applicable. Summary statistics will include number of subjects, mean, standard deviation, minimum, and maximum. Listings for all vital signs will be presented.

Post-dose clinically notable vital signs will be listed and summarized by treatment and dose. Notable abnormalities are indicated in **Table 5** below:

Table 5: Criteria for Clinically Notable Vital Sign Abnormalities

Parameter	High Threshold	Low Threshold
Systolic BP (supine)	> 30 mmHg increase from baseline	> 30 mmHg decrease from baseline
Diastolic BP (supine)	> 20 mmHg increase from baseline	> 30 mmHg decrease from baseline
Heart Rate	> 120 bpm and an increase in HR of ≥ 15 bpm from baseline	< 40 bpm and a decrease in HR of ≥ 15 bpm from baseline
Body Temperature	> 39.0°C ($> 102.2^{\circ}\text{F}$)	< 35.0°C ($< 95.0^{\circ}\text{F}$)

12-Lead ECG: ECG results from the central reader will be used in the analysis. Shift tables summarizing the numbers of subjects shifting from normal pre-dose values to abnormal post-dose values will also be presented. Numeric ECG data will be summarized by treatment group and dose level and mean summary tables, including change from baseline will be presented.

The ECG results will be listed by treatment group and dose level.

Post-dose clinically notable ECGs will be listed and summarized by treatment and dose. Notable abnormalities are indicated in [Table 6](#) below:

Table 6: Criteria for Clinically Notable ECG Abnormalities

Parameter	High Threshold	Low Threshold
PR interval	PR ≥ 220 ms	PR ≤ 120 ms
QRS duration	QRS duration ≥ 120 ms and an increase of ≥ 20 ms from baseline	-
QT interval	QT interval > 500 ms	-
QTcF interval	Men: QTcF interval ≥ 450 ms and an increase of ≥ 60 ms from baseline OR QTcF interval > 500 ms Women: QTcF interval ≥ 470 ms and an increase of ≥ 60 ms from baseline OR QTcF interval > 500 ms	-

Pharmacokinetic Analysis: The plasma concentrations of MW151 will be determined, and used to estimate appropriate PK parameters including C_{max} , T_{max} , AUC, $T_{1/2}$ and K_{el} by non- compartmental analysis. The PK analysis population will include all subjects who received the active study drug and who have sufficient MW151 plasma concentrations to calculate at least 1 PK parameter.

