10.2 CLINICAL LABORATORY TESTING

Summary statistics of observed and change from baseline data will be presented for each treatment group and dose where applicable. Shift tables summarizing the numbers of subjects shifting from normal pre-dose values to abnormal post-dose values will also be presented where applicable. Listings for all safety laboratory assessments will be presented.

Lab tests included will be all in the hematology and coagulation panel, biochemistry panel, and urinalysis panel (as needed lab tests: RBC, WBC, hyaline casts, cellular casts, and granular casts will only be presented as listings).

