10.3 VITAL SIGNS

Vital signs (supine systolic and diastolic blood pressure, orthostatic change in systolic and diastolic blood pressure, supine heart rate/pulse, body temperature) and changes from baseline at each time point will be presented by cohort and treatment group. Listings for all vital signs and orthostatic change will be presented.

Clinically notable vital signs will be listed and summarized by treatment group and dose. Criteria for Clinically Notable vital sign abnormalities are indicated in Table 2 below.

Table 2: Criteria for Clinically Notable Vital Sign Abnormalities

Parameter	High Threshold	Low Threshold
Systolic BP (supine)	> 30 mmHg increase from baseline	> 30 mmHg decrease from baseline
Diastolic BP (supine)	> 20 mmHg increase from baseline	> 30 mmHg decrease from baseline
Heart Rate (supine)	> 120 bpm and an increase in HR of ≥ 15 bpm from baseline	< 40 bpm and a decrease in HR of ≥ 15 bpm from baseline
Body Temperature	> 39.0°C ($> 102.2^{\circ}\text{F}$)	< 35.0°C ($< 95.0^{\circ}\text{F}$)

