10.4 ELECTROCARDIOGRAM MONITORING

ECG parameters (e.g. Ventricular Heart Rate, PR interval, QRS interval, QTc interval, QTcB, QTcF interval, and RR interval) and changes from baseline at each assessment time point will be presented by cohort and treatment group. Listings for ECG parameters will also be presented.

Clinically notable ECGs will be listed and summarized by treatment group and dose. Criteria for Clinically notable ECG abnormalities are indicated in Table 3 below:

Table 3: Criteria for Clinically Notable ECG Abnormalities

Parameter	High Threshold	Low Threshold
PR interval	PR ≥ 220 ms	PR ≤ 120 ms
QRS duration	QRS duration ≥ 120 ms and an increase of ≥ 20 ms from baseline	-
QT interval	QT interval > 500 ms	-
QTcF interval	Men: QTcF interval ≥ 450 ms and an increase of ≥ 60 ms from baseline OR QTcF interval > 500 ms Women: QTcF interval ≥ 470 ms and an increase of ≥ 60 ms from baseline OR QTcF interval > 500 ms	-

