10.6 NEUROLOGICAL EXAMINATIONS

Neurological examinations include mental status, cranial nerves 2-12, motor system and coordination, reflexes, and sensory system. Shift tables summarizing the numbers of subjects shifting from normal pre-dose values to abnormal post-dose values will be created. A listing of abnormal neurological examination data for all subjects will be provided.

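### Repeat and unscheduled results are kept out of all safety summaries, so a subject whose only notable or abnormal post-dose value is unscheduled is listed but not counted

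*Combined protocol and SAP*

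**What the plan says.** The general rule in SAP 7.1 is "Repeat or unscheduled results will not be included in the summaries, but will be listed", repeated word for word in protocol 9.1. The same SAP paragraph makes clear that summaries are not only means: "For categorical variables, the summaries will include frequencies and corresponding percentages".

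The tables that the rule reaches are these:

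- Vital signs, SAP 10.3: "Clinically notable vital signs will be listed and summarized by treatment group and dose".
- ECG, SAP 10.4: "Clinically notable ECGs will be listed and summarized by treatment group and dose". Protocol 9.1 has the matching sentence: "Post-dose clinically notable ECGs will be listed and summarized by treatment and dose".
- Laboratory tests, SAP 10.2: "Shift tables summarizing the numbers of subjects shifting from normal pre-dose values to abnormal post-dose values", with the same table in protocol 9.1.
- Neurological examination, SAP 10.6: "Shift tables summarizing the numbers of subjects shifting from normal pre-dose values to abnormal post-dose values will be created".
- ECG shift tables, which protocol 9.1 also promises.

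None of these sections says whether an unscheduled or repeat value can enter the count.

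On baseline, SAP 7.1 says: "Baseline is defined as the last assessment prior to dosing of study medication". Protocol 6.2.1 permits one repeat per visit of pre-dose vital signs and of ECG abnormalities other than a quantitative QTcF exclusion. It describes how the repeat bears on eligibility, not on analysis. The schedule footnotes and protocol 6.2.1 name the Day -1 triplicate tracing as the ECG baseline.

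**The concern.** Leaving repeats out of by-visit means is ordinary practice, because it keeps one value per subject per visit. A count of subjects who ever crossed a fixed safety threshold serves a different purpose: it should catch any valid crossing after dosing. An ECG or blood pressure taken because a subject felt unwell is unscheduled by nature, and it is the kind of reading most likely to be informative.

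Safety and tolerability are the primary objective. SAP 10.0 assesses them on vital signs, laboratory values, ECGs and examinations as well as adverse events. Protocol 2.3.1 names QTc prolongation and liver enzyme rises among the nonclinical findings. At stake is whether the headline tables for these measures can omit a subject whose crossing is in the database.

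**Working it through.** The plan gives no figure to reproduce here, so the check is mainly of the text, followed by the weight of one subject.

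**1. Does the rule reach the notable counts?** The rule assigns repeat and unscheduled results to the listings and removes them from the summaries. SAP 10.3 and 10.4 call for both a listing and a summary of notable values. Read together, an unscheduled notable value goes into the first and not the second. No exception appears in SAP 7.1, 10.2, 10.3, 10.4 or 10.6, or in protocol 9.1.

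**2. Which subjects are affected?** Hold baseline fixed and classify each dosed subject by whether any scheduled post-dose value crosses and whether any repeat or unscheduled one does.

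- Scheduled crosses, repeat normal: counted under the plan.
- Scheduled crosses, repeat also crosses: counted under the plan.
- No scheduled value crosses, an unscheduled one does: listed, not counted.
- Neither crosses: not counted, correctly.

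The plan's count equals the number with any crossing minus the number in the third group. That last number cannot be negative, so for post-dose values the rule can lower the count but never raise it. The Day 7 laboratory repeats foreseen in protocol 6.2.2 lose nothing, because the scheduled Day 7 value that prompted the repeat stays in.

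**3. Does the schedule leave room for the third group?** From the schedule footnotes, post-dose assessments are:

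- ECG: 1, 2, 4, 12 and 24 h, Day 3, Day 7. Telemetry ends with the 4 h ECG.
- Blood pressure and heart rate: the same times plus 36 h.
- Body temperature: 12, 24 and 48 h, Day 7.
- Safety laboratory tests: Day 2 and Day 7.
- Neurological examination: Day 2 only.

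A reading taken for symptoms between 4 and 12 h, or a temperature taken before 12 h, would be unscheduled. The documents give no rate for such readings, so no expected number can be computed.

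**4. Weight of one such subject.** Each cohort has 6 MW151 and 2 placebo subjects. With five cohorts, pooled placebo is 5 × 2 = 10.

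- One dose level: 1/6 = 16.7 percentage points.
- Pooled placebo: 1/10 = 10 points.

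These are for a denominator of all dosed subjects in the group. The documents do not state the shift-table denominator. If it were only subjects with a normal baseline, and five of six qualified (an assumption), the weight would be 1/5 = 20 points.

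**5. Pre-dose repeats.** The baseline definition, read literally, selects a valid repeat, since that is the last assessment before dosing. For ECG, no Day 1 pre-dose tracing is scheduled, so the Day -1 triplicate is ordinarily also the last one. Protocol 6.2.1 bars repeating ECGs or safety laboratory tests that meet a quantitative exclusion criterion. What remains is mainly vital signs, where a programmer might wrongly carry the exclusion over to baseline. With assumed pre-dose systolic readings of 152 and then 140 mmHg, a later 172 is +20 from the first and +32 from the repeat, against a threshold of more than 30. A later 120 is -32 from the first and -20 from the repeat. One confirming sentence prevents this.

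**The case against.** The strongest reply is that little is lost in practice. A repeat usually follows a scheduled abnormal value, and that value stays counted, so a reassuring repeat cannot erase it. Scheduled coverage is dense, and the protocol plans no post-dose unscheduled ECGs or vital signs. The 1/6 figure is the weight of any one subject and does not measure how often the problem occurs. No decision depends on these tables: the analysis is descriptive, and the halting criteria in protocol 8.1 rest on adverse events and clinical judgment. All of this stands, and it sets the size of the point.

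It does not change what the rule does. The adverse event route depends on the investigator judging a finding clinically significant, whereas the notable tables apply fixed thresholds. SAP 7.1 does say that calculations use the data available, but that sentence is in the missing-data paragraph and does not mention repeats.

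A reader might infer more than the documents support:

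- *That the comparison with placebo is biased.* The rule is the same in both groups, and nothing in the documents supports a claim of distortion.
- *That baseline is undefined.* The definition already points to the repeat, and the ECG baseline is named.
- *That Early Termination data are dropped.* These assessments are specified in the protocol as the Day 3 procedures, so they are not naturally read as unscheduled.
- *That worsening from an abnormal laboratory baseline is hidden.* Entry does allow ALT or AST up to 1.5 times the upper limit of normal if not clinically significant, and the named shift table starts from normal. Worsening at scheduled visits still shows in the change from baseline and the maximum, and all values are listed. The shift format is largely a display choice.

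**Conclusion.** The point holds as a cheap improvement. As written, the rule leaves a subject whose only post-dose crossing or abnormality is unscheduled out of the notable-value and shift tables, and for post-dose values it can only undercount. One such subject is 16.7 points at a dose level of six, or 10 points in a pooled placebo group of ten, if the planned numbers are dosed and all are in the denominator. The frequency is unknown and may be zero.

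The effect is confined to these table counts. Nothing is lost from the listings, clinically significant post-dose findings are still recorded as adverse events, and the DSMB still reviews all the safety data it has. Dose escalation and halting are not shown to be affected.

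**What to change.** In SAP 7.1, limit the exclusion to by-visit descriptive statistics and add wording such as:

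*All valid post-dose results through the end of the subject's study follow-up, scheduled or not, count in the notable-value and shift tables. Each subject is classified by the worst post-dose value, in each direction where both a high and a low threshold apply. Technically invalid tracings or samples are excluded.*

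Add a table footnote that subjects with more unscheduled tests have more chances to be flagged; this is the real downside of the change.

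Three confirming statements would remove doubt: that a valid pre-dose vital-sign repeat serves as baseline, that the Day -1 triplicate remains the ECG baseline, and that Early Termination assessments count as scheduled. A laboratory shift grid of baseline category (low, normal, high) by worst post-dose category is optional.

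The cost is a few SAP sentences and minor table programming, with no new data. The change should be made before the SAP is signed off, which protocol 9.1 places ahead of database lock. Protocol 9.1 describes general approaches and leaves detail to the SAPs, so its sentence can be aligned if the protocol is next amended, with the written Sponsor and IRB approval that protocol 6.3.2 requires.
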